1 INTRODUCTION

There are no major changes to the analyses described in the protocol.

1.1 STUDY DESIGN

This is a multinational, randomized, placebo-controlled, double-blind, Phase 2a proof-of-concept study. The purpose of this study is to evaluate the efficacy, safety, PK, biological effects of SAR442970 compare with placebo in adult participants with moderate to severe hidradenitis suppurativa (HS).

The study is composed of 3 parts: a double-blind, placebo-controlled period (Period A), followed by an open-label period (Period B), and then a safety Follow-up Period (Period C). After a screening period of 2 to 4 weeks, participants will receive SAR442970 150 mg or matching placebo Q2W at the Week 0 visit up to the Week 14 visit as part of Period A. Beginning at the Week 16 visit, all participants will receive SAR442970 150 mg Q2W up to the visit prior to the individual participant's end of treatment (EOT) visit as part of Period B. Period C will commence with the End of Treatment (EOT) visit and conclude with the End of Study (EOS) visit. For participants in the US, response will be assessed at the Week 20 visit (see definition of response in [Section 2.2.1](#)). Responders at Week 20 will continue in Period B to complete the 12-week open-label period. Non-responders at Week 20 will move directly to the safety follow-up period (Period C) with the Week 20 visit serving as their EOT visit.

Approximately 84 participants will be randomized in a 2:1 ratio to SAR442970 150 mg Q2W or matching placebo. Randomization will be stratified by HS treatment history (biologic and small molecule immunosuppressive-naïve or TNF-experienced) and Hurley stage (II or III). The recruitment target is approximatively 66 biologic and small molecule immunosuppressive-naïve and approximatively 18 TNF-experienced. Within the biologic and small molecule immunosuppressive-naïve subgroup, the number of participants with Hurley Stage III is not to exceed more than 50%. Within the biologic and small molecule TNF-experienced subgroup, the number of participants with Hurley Stage III is not to exceed more than 50%.

The primary analysis population is the biologic and small molecule immunosuppressive-naïve subgroup. Efficacy objectives and endpoints will be evaluated in an exploratory manner in the TNF-experienced subgroup.

1.2 OBJECTIVES AND ENDPOINTS

Table 2 - Objectives and endpoints

Objectives	Endpoints
Primary	

To evaluate the efficacy of SAR442970 during the double-blind, placebo-controlled period in the biologic and small molecule immunosuppressive-naïve subgroup of participants with HS	
The clinical response as measured by the percentage of biologic and small molecule immunosuppressive-naïve participants achieving Hidradenitis Suppurativa Clinical Response

Objectives	Endpoints

Secondary
 
• To evaluate the efficacy and safety of SAR442970 in the biologic and small molecule immunosuppressive-naïve subgroup of participants with HS• To evaluate the effect of SAR442970 on pain in the biologic and small molecule immunosuppressive-naïve subgroup of participants with HS• To evaluate the pharmacokinetics (PK) of SAR442970 and anti-drug antibodies (ADA) to SAR442970 in the biologic and small molecule immunosuppressive-naïve subgroup of participants with HS	
(HiSCR50) (defined as ≥ 50% reduction from Baseline in the total abscess and inflammatory nodule [AN] count, with no increase from Baseline in abscess or draining tunnel count) at Week 16
 
• Time to onset of achieving HiSCR50• Percentage of participants achieving HiSCR75 (defined as ≥ 75% reduction from Baseline in the total AN count, with no increase from Baseline in abscess or draining tunnel count) at Week 16• Percentage of participants achieving HiSCR90 (defined as ≥ 90% reduction from Baseline in the total AN count, with no increase from Baseline in abscess or draining tunnel count) at Week 16• Percentage of participants who experience improvement by at least one International Hidradenitis Suppurativa Severity Score System (IHS4) stage at Week 16 (See also Section 2.3.2 for definition of IHS4)• Change in absolute score from Baseline in IHS4 at Week 16• Percentage of participants who experience a flare, defined as at least a 25% increase in AN count (with a minimum increase of 2) relative to Baseline at Week 16 (See also Section 2.3.4.1 for definition of flare)• Percentage of participants achieving IHS4-55 at Week 16 (defined as achievement of a 55% reduction in IHS4 score from Baseline)• Incidence of treatment-emergent adverse events (TEAEs), adverse events of special interest (AESIs), and serious adverse events (SAEs) including local reactions• Incidence of potentially clinically significant abnormalities in laboratory tests, vital signs, and electrocardiograms• Percentage of participants achieving at least 30% reduction and at least 1 unit reduction from Baseline in weekly average of daily [REDACTED] [REDACTED] [REDACTED] [REDACTED] [REDACTED]• Serum SAR442970 concentrations throughout the study• Incidence of anti-SAR442970 antibody positive response throughout the study

Objectives	Endpoints
Exploratory	

• To evaluate the effect of SAR442970 on quality of life in participants with HS	
• [REDACTED]• [REDACTED] DLQI [REDACTED]• [REDACTED] DLQI ≥4

Objectives	Endpoints

1.2.1 Estimands

Primary estimand defined for main endpoints are summarized [Table 3](#) below. More details are provided in [Section 2](#). Additional secondary objectives/endpoints are not included in this table but would be handled with a similar strategy as the endpoint type (i.e., continuous, proportion, or time-to-event). For all these estimands, the comparison of interest will be the comparison of SAR442970 vs. placebo.

Table 3 - Summary of estimands for the primary and selected secondary endpoints

Endpoint Category	Estimands			
	Endpoint(s)	Population	Intercurrent event(s) handling strategy	Population-level summary and missing data handling
Primary objective: To evaluate the efficacy of SAR442970 during the double-blind, placebo-controlled period in the primary analysis population of the biologic and small molecule immunosuppressive-naïve subgroup participants with moderate to severe HS.				
Primary endpoint-Proportion	Percentage of participants achieving HiSCR50 at Week 16	Biologic and small molecule immunosuppressive-naïve population of Period A	
The following intercurrent events (IEs) will be handled with the composite variable strategy; participants will be considered as non-responders after such IE.
 
 Starting or increase in dose of oral antibiotic therapy for HS prior to Week 16. Starting selected prohibited medications^a. Discontinuation of study intervention due to lack of efficacy. 
The following IEs will be handled with the treatment policy strategy (without IE that need to be handled with composite variable strategy). Data collected after starting such IE will be included.
 
 Starting other prohibited medications. Discontinuation of study intervention due to reasons other than lack of efficacy. 	
The statistical analysis will be conducted using a Bayesian logistic regression model that includes the treatment group and stratified by baseline Hurley Stage. An informative prior on the placebo response rate will be used, based on the available historical studies.
 
The difference of response rates between SAR442970 and placebo along with the 80% and the 90% credible intervals will be derived.
 
Missing data will be imputed as non-responder.

Secondary objective: To evaluate the efficacy and safety of SAR442970 in the biologic and small molecule immunosuppressive-naïve subgroup of participants with HS.				
Secondary endpoint- Time-to-event	Time to onset of achieving HiSCR50	Biologic and small molecule immunosuppressive-naïve population of Period A	
The following IE will be handled with the composite variable strategy; analysis will be censored at Week 16:
 
 Starting or increase in dose of oral antibiotic therapy for HS prior to Week 16 Starting selected prohibited medications prior to Week 16^a. 	
This time-to-event endpoint will be analyzed using a Cox proportional hazards model that includes treatment group and stratified by baseline Hurley Stage.

Endpoint Category	Estimands			
	Endpoint(s)	Population	Intercurrent event(s) handling strategy	Population-level summary and missing data handling
Secondary endpoint- Proportion	Percentage of participants who experience improvement by at least one in IHS4 stage at Week 16	Biologic and small molecule immunosuppressive-naïve population of Period A	
 Discontinuation of study intervention due to lack of efficacy. 
The following IEs will be handled with the treatment policy strategy (without IEs that need to be handled with composite variable strategy). Data collected after starting such IE will be included.
 
 Starting other prohibited medications. Discontinuation of study intervention due to reasons other than lack of efficacy. 	
The hazard ratio along with the 80% and 90% confidence intervals will be reported.
 
Analyses will be censored at the time of last HS clinical parameter assessment.

Endpoint Category	Estimands			
	Endpoint(s)	Population	Intercurrent event(s) handling strategy	Population-level summary and missing data handling
Secondary endpoint- Continuous	Change in absolute score from baseline in IHS4 at Week 16	Biologic and small molecule immunosuppressive-naïve population of Period A	
The following IEs will be handled with the composite variable strategy; data after the IE will be excluded from the analysis, and the participant's worst post-baseline value (WOCF) on or before the time of the IE will be assigned to the Week 16 value. For participants with no post-baseline value, the baseline value will be used.
 
 Starting or increase in dose of oral antibiotic therapy for HS during the treatment period. Starting selected prohibited medications^a. Discontinuation of study intervention due to lack of efficacy. 
The following IEs will be handled with the treatment policy strategy (without IEs that need to be handled with composite variable strategy). Data collected after starting such IE will be included.
 
 Starting other prohibited medications. Discontinuation of study intervention due to reasons other than lack of efficacy. 	
Analysis of covariance (ANCOVA) including the baseline value, treatment group and stratified by baseline Hurley Stage.
 
The difference of the SAR442970 group against placebo in mean response and the corresponding the 80% and 90% confidence intervals will be provided.
 
Participants with missing data will be imputed with participants' WOCF. For participants with no post-baseline value, the baseline value will be used.

Secondary objective: To evaluate the effect of SAR442970 on pain in the biologic and small molecule immunosuppressive-naïve subgroup of participants with HS				
Secondary endpoint- Skin pain	
Percentage of participants achieving at least 30% reduction and at least 1 unit reduction from Baseline in weekly average of daily HS Skin Pain NRS at Week 16 among participants with Baseline NRS = 3 (HS-Skin Pain NRS is based on worst skin pain in a 24-hour recall period [daily assessment is averaged over 7-day period])
	Biologic and small molecule immunosuppressive-naïve population of Period A	
The following IEs will be handled with the composite variable strategy; participants will be considered as non-responders after such IE.
 
 Using analgesic therapy within 5 days of Week 16 will be considered as non-responders Discontinuation of study intervention due to lack of efficacy. 
The following IE will be handled with the treatment policy strategy (without IEs that need to be handled with
	
CMH method including treatment group and stratified by baseline Hurley Stage.
 
The difference of the response rates between SAR442970 and placebo and the 80% and 90% confidence intervals will be derived.
 
Participants with missing data will be imputed as non-responder.

Endpoint Category	Estimands			
	Endpoint(s)	Population	Intercurrent event(s) handling strategy	Population-level summary and missing data handling
			
composite variable strategy). Data collected after starting such IE will be included.
 
• Discontinuation of study intervention due to reasons other than lack of efficacy.	

a The list of medications will be selected by blinded medical review prior to database lock. Participants that receive the selected treatment will also be reviewed in a blinded fashion to make sure the medication was used due for HS treatment failure and not an unrelated condition.

1.3 ANALYSIS POPULATIONS

Participants exposed to study intervention before or without being randomized will not be considered randomized and will not be included in any analysis population. The safety experience of these participants will be reported separately.

Randomized participants for whom it is unclear whether they took the study intervention will be considered as exposed and will be included in the safety population as randomized.

For participants receiving more than one study intervention during the study, the intervention group for as-treated analyses will be SAR442970 150 mg q2w if the participant received at least one administration of SAR442970.

The following populations for analyses are defined. The primary population of the efficacy endpoints will be the biologic and small molecule immunosuppressive-naïve population.

Table 4 - Populations for analyses

Period	Population	Description
Period A and Period B	Screened	All participants who signed the ICF.
	Randomized	All participants from screened population who have been allocated to a randomized intervention by IRT regardless of whether the intervention was received or not.
Period A		
	Modified ITT (mITT) of Period A	All randomized participants who have taken at least 1 dose of study intervention of Period A. Participants will be analyzed according to the intervention allocated by randomization. Randomized participants for whom it is unclear whether they took the study medication will be included.
	Biologic and small molecule immunosuppressive-naïve of Period A	All randomized participants in the biologic and small molecule immunosuppressive-naïve subgroup who have taken at least 1 dose of study intervention of Period A. Participants will be analyzed according to the intervention allocated by randomization. Randomized participants for whom it is unclear whether they took the study medication will be included.
	TNF-experienced of Period A	All randomized participants in the TNF-experienced subgroup who have taken at least 1 dose of study intervention of Period A. Participants will be analyzed according to the intervention allocated by randomization. Randomized participants for whom it is unclear whether they took the study medication will be included.
	Safety of Period A	All randomized participants who have taken at least one dose of study intervention of Period A, regardless of the amount of intervention administered.

	Participants will be analyzed according to the intervention they actually received. For participants who receive at least one dose of SAR442970, the actual intervention allocation for as-treated analysis will be the SAR442970 group.
Pharmacokinetics (PK) of Period A	All participants from the safety population of Period A with at least one post-Baseline PK result. Participants having received only placebo will not be part of the PK population. Participants will be analyzed according to the intervention they actually received. For participants who receive at least one dose of SAR442970, the actual intervention allocation for as-treated analysis will be the SAR442970 group.
Biomarker PD of Period A	All participants from the safety population of Period A with biomarker results available at baseline and at least one post-baseline visit. Participants will be analyzed according to the intervention they actually received. Randomized participants for whom it is unclear whether they took the study medication will be included.
Biomarker predictive of Period A	All participants from the safety population of Period A with a baseline biomarker result. Participants will be analyzed according to the intervention they actually received. Randomized participants for whom it is unclear whether they took the study medication will be included.

Period B

miITT of Period B	All randomized participants who continue in Period B and have taken at least 1 dose of study intervention in this period. Randomized participants for whom it is unclear whether they took the study medication will be included.
Biologic and small molecule immunosuppressive-naïve of Period B	All randomized participants in the biologic and small molecule immunosuppressive-naïve subgroup who continue in Period B and who have taken at least 1 dose of study intervention of Period B. Randomized participants for whom it is unclear whether they took the study medication will be included.
TNF-experienced of Period B	All randomized participants in the TNF-experienced subgroup who continue in Period B and who have taken at least 1 dose of study intervention of Period B. Randomized participants for whom it is unclear whether they took the study medication will be included.
Safety of Period B	All randomized participants who continue in Period B and who have taken at least one dose of study intervention of Period B, regardless of the amount of intervention administered. Participants will be analyzed according to the intervention they actually received.
Pharmacokinetics (PK) of Period B	All participants from the safety population of Period B with at least one post-Baseline PK result. Participants will be analyzed according to the intervention they actually received.
Biomarker PD of Period B	All participants from the safety population of Period B with biomarker results available at baseline and at least one post-baseline visit.

		Participants will be analyzed according to the intervention they actually received. Randomized participants for whom it is unclear whether they took the study medication will be included.
	Biomarker predictive of Period B	All participants from the safety population of Period B with a baseline biomarker result. Participants will be analyzed according to the intervention they actually received. Randomized participants for whom it is unclear whether they took the study medication will be included.
Period A and Period B	Antidrug antibody (ADA)	All participants from the safety population treated with SAR442970 with at least one post-Baseline ADA result (positive, negative, or inconclusive). Participants will be analyzed according to the intervention they actually received.

Abbreviations: ADA=anti-drug antibody; ICF=informed consent form; IRT= interactive response technology; PK=pharmacokinetic(s); PD=Pharmacodynamic(s); TNF=tumor necrosis factor.

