### **Number of participants:**

The study will include approximately 84 adult participants with moderate to severe HS stratified based on prior treatment experience (approximately 66 biologic and small molecule immunosuppressive-naïve and approximately 18 TNF-experienced).

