**Table 6 - Study arm(s)**

|                        |   |   |
|------------------------|---|---|
| Arm title       | SAR442970 150 mg  | Placebo   |
| Arm type        | Experimental  | Placebo   |
| Arm description | Participants will receive 150 mg of SAR442970 Q2W to complete 14 total doses (or 28 weeks of treatment with SAR442970). | Participants will receive placebo Q2W to complete 8 total doses of placebo (or 16 weeks of treatment with placebo), then 150 mg of SAR442970 Q2W to complete 6 total doses (or 12 weeks of treatment with SAR442970). |

Abbreviations: Q2W=once every 2 weeks

For a regional or national emergency declared by a governmental agency that results in travel restrictions, confinement, or restricted site access, contingency measures are included in Appendix 9 ([Section 10.9](#): Contingency measures for a regional or national emergency that is declared by a governmental agency).

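### The SAP's as-treated rule does not limit the qualifying SAR442970 dose to Period A; read literally, it moves every crossed-over placebo participant into the active column of the Period A safety tables

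*SAP*

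**What the plan says.** SAP 1.3 gives a general rule ahead of Table 4, for participants given more than one intervention at any time in the study: "the intervention group for as-treated analyses will be SAR442970 150 mg q2w if the participant received at least one administration of SAR442970". The trigger is the whole study, not a period.

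In Table 4, the Safety of Period A row defines membership by a Period A dose: "All randomized participants who have taken at least one dose of study intervention of Period A, regardless of the amount of intervention administered". It then groups participants by what they actually received and adds: "For participants who receive at least one dose of SAR442970, the actual intervention allocation for as-treated analysis will be the SAR442970 group". The PK of Period A row carries the same added sentence and leaves out participants who had only placebo. In both rows the period is named for entry, but not for the dose that decides the group.

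The design has a planned switch. SAP 1.1 states: "Beginning at the Week 16 visit, all participants will receive SAR442970 150 mg Q2W". Protocol Table 6 gives the placebo arm eight placebo doses, "then 150 mg of SAR442970 Q2W to complete 6 total doses (or 12 weeks of treatment with SAR442970").

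SAP 2.1 names the display groups: SAR442970 and Placebo for Period A; for Periods B and C, a continuing SAR442970 group and a Placebo/SAR442970 group.

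**The concern.** A rule of the form *any active dose makes the participant active* is common in parallel-group trials, where a placebo participant gets active drug only by mistake. Here active drug is the planned second stage for the placebo arm. A placebo participant who enters Period B has received two interventions during the study by design, and so meets the trigger in SAP 1.3.

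Period A is the only placebo-controlled part of the trial, and the incidence of TEAEs, SAEs and AESIs is a secondary endpoint. If the rule were programmed as it stands, the Period A safety tables would set a pooled column, holding most of both arms, against a small placebo column made up only of people who never started open-label treatment. The first column would dilute any difference, and the second would be selected on early exit.

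Two further Period A analyses are exposed:
- **PK.** A crossed-over placebo participant has not received only placebo over the whole study, so the exclusion in the PK row no longer clearly removes that person.
- **Biomarkers.** The Biomarker PD population is grouped by intervention actually received and feeds the SAR442970-versus-placebo repeated-measures model in SAP 2.8.3.2. The general rule in SAP 1.3 covers all as-treated analyses.

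**Working it through.** **Inputs**
- Total and ratio (SAP 1.1): "Approximately 84 participants will be randomized in a 2:1 ratio to SAR442970 150 mg Q2W or matching placebo".
- Subgroups (Protocol synopsis): "approximately 66 biologic and small molecule immunosuppressive-naïve and approximately 18 TNF-experienced".
- Dosing (Protocol Table 6): the placebo arm has 8 placebo doses, then 6 SAR442970 doses.
- Share of placebo participants who never receive open-label drug, *d*: not given in the documents. Assumed range 0% to 30%.

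**Step 1: reproduce the plan's figures.** 66 + 18 = 84, as stated. At 2:1, 84 × 2/3 = 56 SAR442970 and 84 × 1/3 = 28 placebo (44 and 22 in the naïve subgroup, 12 and 6 in the TNF-experienced subgroup). Dosing every 2 weeks from Week 0 to Week 14 is 8 doses, and from Week 16 to Week 26 is 6, matching Table 6.

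**Step 2: who meets the trigger.** Any placebo participant with at least one open-label dose. That includes US participants who stop as non-responders at Week 20, because they are still dosed at Weeks 16 and 18. The timing of the early analysis does not help: Protocol 9.4 places it after the last participant completes 16 weeks, and open-label dosing starts at the Week 16 visit.

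**Step 3: apply the rule literally.** Number moved = 28 × (1 − *d*), rounded. Active column = 56 + moved. Placebo column = 28 − moved.

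| *d* (assumed) | Moved | Active column | Placebo column | Share of active column given only placebo in Period A |
|---|---|---|---|---|
| 0% | 28 | 84 | 0 | 28/84 = 33% |
| 5% | 27 | 83 | 1 | 27/83 = 33% |
| 10% | 25 | 81 | 3 | 25/81 = 31% |
| 20% | 22 | 78 | 6 | 22/78 = 28% |
| 30% | 20 | 76 | 8 | 20/76 = 26% |

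**Step 4: apply the rule to Period A doses only.** With no dosing errors the planned columns are 56 and 28.

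**Step 5: what the moved participants contribute.** SAP 2.1 closes the Period A treatment-emergent window no later than the first open-label dose. Their Period A events are therefore all placebo-period events. As an illustration only, with assumed event rates of 60% on SAR442970 and 40% on placebo, and *d* = 10%, the active column would show (56 × 0.60 + 25 × 0.40)/81 = 43.6/81 = 53.8% instead of 60%.

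**Step 6: the same rule in Periods B and C.** Applied across the study, it would also take the crossed-over participants out of the Placebo/SAR442970 group, which exists to hold them.

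**The case against.** The strongest reply is that the SAP, read as a whole, does not intend this.
- The one-dose sentence stands only in the Safety and PK rows for Period A. The matching Period B rows say just that participants are analysed by what they received. This pattern fits a rule for wrong or mixed dosing within Period A.
- The populations are defined by period (Protocol 9.1, SAP Table 4), and SAP 2.7 analyses the periods separately.
- The Period A windows end at the first open-label dose, and Period A exposure and compliance are built on blinded administrations.
- The Placebo/SAR442970 group in SAP 2.1 makes no sense if crossed-over participants count as plain SAR442970.
- The Period A biomarker model compares SAR442970 with placebo, which presupposes a placebo group.

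A table with about 81 active and 3 placebo participants in a 2:1 trial of 84 would also be noticed at first review. Safety analyses are descriptive with no testing, and the Period A efficacy populations are analysed as randomised.

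All of this stands as evidence of intent, and it limits the consequence. It does not supply the missing limit: no sentence in either document says that only Period A doses count. What remains is an explicit assignment rule that has to be overridden by inference from other sections.

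**Conclusion.** The rule in SAP 1.3, and its repetition in the Safety and PK rows of Period A, lacks a period limit and contradicts the grouping in SAP 2.1. Followed as written, it gives wrong Period A safety columns: between 84 vs 0 and 76 vs 8 instead of 56 vs 28, for an assumed 0% to 30% of placebo participants never reaching open-label drug. These counts rest on the planned enrolment, exact 2:1 allocation, no dosing errors and that assumed range.

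A reader might go further and infer that the SAP abandons the controlled safety comparison, or that the Period A tables will be wrong. The documents do not support that. The loss follows only from mechanical application, and several of the SAP's own provisions point to a rule meant for mixed dosing within Period A. Nor do they support any effect on the primary or secondary efficacy results.

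The point is still more than editorial. The text that a programmer would follow for group assignment gives a wrong answer rather than no answer, in the only placebo-controlled safety comparison.

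**What to change.** - In SAP 1.3 and in the Safety and PK of Period A rows of Table 4, make the condition: *at least one administration of SAR442970 during Period A (before the first open-label IMP administration)*.
- In the PK of Period A row, apply the same limit to the exclusion of participants who had only placebo, so that it means only placebo during Period A.
- Add one sentence stating that the groups for Periods B and C follow the sequence groups in SAP 2.1.

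This restores the planned 56 vs 28 and still deals with a placebo participant given SAR442970 by mistake in Period A. It costs a few words in the SAP, with no change to the data collected, the sample size or any other analysis.
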